The Principal Investigator will ensure that subject identification codes are kept for at least fifteen years after the trial has been completed or discontinued.

The data of all the CRDs will be entered into a database created for this purpose and equipped with safety margins and internal coherence standards. This database will be equipped with a double entry system and filters that prevent and detect any type of inconsistency or error in it. The information will be validated through internal consistency controls, studying the missing values. The data will be verified and corrected until the

database is fully validated. Once the database is purged, the variables will be recoded generating new variables (regrouping, sums, etc.).

- **Sample size.**

The hypothesis of this study was that the risk of postoperative complications at 90 days in the ND group would not be higher than in group D. A non-inferiority configuration was selected because the omission of drain placement is advantageous in terms of relieving to patients from discomfort and a decrease in medical cost. In calculating the sample size, the risk of an early postoperative complication related to LT was assumed to be 9% in the drain group and 6% in the no-drain group according to the literature review performed. Under a 4% non-inferiority margin, an alpha error of 0.05, and a statistical power of 80%, the sample was calculated as 174 patients in each arm. Assuming a 5% dropout rate, a total of 365 patients will be recruited into this study.

- **Statistic analysis**

The subsequent statistical analysis will be performed with the SPSS v.25 software.

- **Descriptive analysis.**

The demographic data and other baseline characteristics of the trial subjects will be described using descriptive statistical indices, for the overall number of patients and for each of the groups of patients under study. Continuous variables will be described using measures of central tendency (mean) and measures of dispersion (standard deviation). While the categorical variables will be described through absolute and relative frequency tables. The baseline characteristics shown by the groups of participants included in the study will be compared. Statistical tests will be performed depending on the nature of the variables. To study the relationships between variables, standard chi-square tests have been used in the case of qualitative variables and Pearson's correlation in the case of quantitative variables. In each situation, any association in which the p-value was less than 0.05 was considered statistically significant. The magnitude of the association between qualitative variables will be made by calculating the relative risk, and between quantitative

variables using Pearson's correlation coefficient. In this multivariate analysis, the odds ratios will be obtained with a 95% confidence interval.

- **Analysis of the main variable**

The primary efficacy criterion is the comparison of the incidence of postsurgical complications according to the Clavien-Dindo classification.

- **Secondary variables analysis**

The univariate and multivariate study of all the included variables will be carried out.

- **ETHICS**

This study will be carried out in European hospitals in accordance with current European legislation that regulates the performance of clinical trials, for which this protocol is established as a reference document for review by the Ethics Committees, as well as for the taking of practical decisions in the management of included patients by participating investigators. The study will only begin after obtaining written authorization from the Clinical Research Ethics Committee.

With the exception of those emergency situations, no protocol changes or deviations will be allowed without documented approval. The CEIC must be informed of the possible changes and will approve in writing any change or deviation that may increase the risks of the subject and / or may adversely affect the rights of the volunteer or the validity of the research. This stipulation does not apply to those changes that are made to reduce inconvenience or avoid risks to the subjects and to changes that affect the administrative aspects of the study. Carrying out this study will respect at all times the rules of Good Clinical Practice and the regulations and recommendations that appear in the Declaration of Helsinki and that are included in the current legislation on the practice of clinical trials.

- **INFORMED CONSENT**

Before any specific test or study procedure is carried out, patients (or witnesses or legal representatives) who meet the participation criteria will be asked to sign the informed consent document approved by the Ethics Committee. Sufficient time should be given to them to review the informed consent document and to have their questions answered

before signing. Each individual will be informed orally and in writing of the study methodology, as well as the possible undesirable effects that may appear as a consequence of the different determinations that will be made. In the same way, they will be informed of the voluntary nature of the study both in terms of their participation and in terms of abandonment at any time during the study. Likewise, everyone will be aware of the possible undesirable effects that may appear during the study, regardless of the assigned group. All of them will sign an informed consent to participate in the project.

- **DIRECT ACCESS TO SOURCE DATA / DOCUMENTS**

Source documents are all original documents, data and records. All the data collected to carry out the study, both for the preparation of the subject's Clinical History, and for the rest of the study documents, will be archived in the participating centers, on paper or in digital format, in accordance with the procedures of each center. The data collected for the study will be identified by a numerical code and only the principal investigator / collaborators will be able to relate said data with the patient and with their medical history.

Access to the information of the participating subjects will be restricted to the study doctor and authorized collaborating team members. The researcher and the center will guarantee direct access to the data or source documents to the personnel authorized by the promoter (monitor, auditor), to the health authorities (Spanish Agency for Medicines and Health Products), and to the Ethical Committee for Clinical Research, when need it.

- **DATA MANAGEMENT AND RECORDS FILE**

Patient data will be collected in a CRD. The principal investigator or a sub-investigator of the center must ensure the accuracy and completeness of the data recorded and put their signature on the corresponding CRDs. These data will be exported to REDCap, which will be the platform on which all the data from the centers participating in the trial will be shared.

When the database has been considered complete and accurate, it will be closed by locking the database. The filing of all relevant documents in relation to the study will be

carried out according to the requirements of the ICH-GCP, Commission directive 2005/28 / EC of April 8, 2005, and according to the pertinent national laws.

- **DATA PROTECTION**

The data will be included in a database that must comply with Regulation 679/2016, of April 27, General Data Protection Regulation and Organic Law 3/2018, of December 5, on the Protection of Personal Data and guarantee of digital rights. Likewise, the transmission of said data will be done with the appropriate security measures in compliance with said regulation. During documentation and analysis, patients will only be identified by their individual patient code, while all subject names will be kept secret by the investigator.

- **FINANCING AND INSURANCE**

No extraordinary financing is necessary, since we will use available resources in daily clinical and surgical activity. This study would be exempt from the need to take out insurance since the patients will undergo two surgical techniques performed in routine clinical practice and do not pose an additional risk to the patient.

- **PUBLICATION POLICY**

Each researcher is free to publish data from their center. However, the collected data will be presented and published by the appropriate author according to the criteria established by the International Committee of Medical Journal Editors (ICJME). Data will be published regardless of trial results.

- **BIBLIOGRAPHY**

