PROTOCOL

TITLE:

Abdominal drainage in the postoperative period of liver transplantation (DRALIT):
multi-institutional randomized clinical trial

Drenaje abdominal en el postoperatorio del trasplante hepático (DRALIT): Ensayo Clínico
multicéntrico aleatorizado.

Protocol code:

Version: v.1

Date: 24/5/2022

EudraCT:

PROMOTER: Department of General Surgery and Digestive Diseases

PRINCIPAL RESEARCHER / COORDINATOR: [name] / [name]

CONFIDENTIAL

This document contains confidential information that should not be disclosed or published to other people other than clinical researchers, members of the Clinical Research Ethics Committees of the participating hospital centers and Spanish Health Authorities.

ABSTRACT

Title:

Abdominal DRAINage in the postoperative period of Liver Transplantation (DRALIT): multi-institutional randomized clinical trial

Promoter: Department of General Surgery and Digestive Diseases

Principal researchers:

[name]. FEA General and Digestive System Surgery Service. Virgen de la Arrixaca University Clinical Hospital.

[name]. General Surgery and Digestive System Resident. Virgen de la Arrixaca University Clinical Hospital.

Justification of the study: Classically, in the postoperative period of liver transplantation (LT), abdominal drainage has been used as a way to make the early diagnosis of hemorrhages, bile leaks and other postsurgical complications, as well as an evacuation route for ascites. The use of it routinely is currently under discussion due to the morbidities associated with its use.

Objectives: The objective of the clinical trial is to evaluate whether the routine use of abdominal drainage in the postoperative period of LT is associated or not with an increase in postoperative complications. Also evaluate the quality of life in relation to the presence or not of abdominal drainage.

Trial design: After signing the informed consent of those patients who meet the inclusion criteria, they will be randomized into two groups for placement of an abdominal drain or not. On the third day, the abdominal drainage will be removed except for signs of bleeding, postoperative infection or bile leakage, and abdominal postoperative complications will be evaluated according to the Clavien-Dindo scale in the first 90 postoperative days.

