In transplant patients, the use of post-surgical abdominal drains on a routine basis has shown an increase in total protein losses in patients with refractory ascites, an increase in ascending infections secondary to drainage, infection and pain at the insertion point of the drain, as well as as, an increase in hospital stay. Nor can a higher rate of postsurgical bleeding and bile leakage be ruled out in patients with abdominal drainage.

Currently, in the few studies that there are in reference to the systematic use of abdominal drains in ITH, the need for them prophylactically is being discussed as an early diagnosis of postoperative intra-abdominal complications is not observed, but complications are seen to increase secondary to drainage. Therefore, the need to use it systematically in all patients is currently under discussion.

Currently, we are facing an increase in ERAS® (Enhanced Recovery After Surgery) programs, which began in 2008 with colorectal surgery and are currently expanding to other surgical procedures. These programs advocate reducing the number of drains and even not using them in patients with a low risk of post-surgical complications.

In the current bibliography, the methodology of the studies is varied, with the majority being non-randomized retrospective studies, which is why it is a subject that requires studies with a better methodological design and a higher number of patients to obtain

conclusions of clinical relevance. that can set the direction in this area that is in constant discussion.

Given the absence of any randomized non-inferiority clinical trial that studies the routine use of abdominal drainage in the postoperative period of liver transplantation, we consider that it is necessary to carry it out to increase the evidence.

The number of HT performed in each center is limited and variable annually, which is why we consider that the best design for this clinical trial is a European multicenter.

- **OBJECTIVE AND PURPOSE OF THE TEST**

The objective of our randomized clinical trial is to evaluate whether the prophylactic use of intra-abdominal drains in LT patients reduces postoperative intra-abdominal complications, compared to their routine use.

- **Main goal.**
 - To assess whether the prophylactic use of abdominal drains in the postoperative period of LT increases the number of abdominal complications in the 90 postoperative days (Clavien-Dindo)
- **Secondary objectives.**

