 - To evaluate the possible improvement in the quality of life of the transplanted patient derived from the absence of postsurgical drainage (SF-36).
 - Evaluate the postoperative stay in both groups.

- **STUDY DESIGN**

Unmasked European multicenter randomized clinical trial with two arms parallel to the study.

Patients who meet the inclusion criteria will be offered to participate in this study by signing an informed consent. An informed consent approved by the Research Ethics Committee of the Virgen de la Arrixaca University Hospital will be used.

Patients who give their consent for the study will be randomized to the drainage group (D) and the control group without drainage (ND) before the beginning of the abdominal wall closure.

In the drainage group (D), it will be placed on the right flank / right iliac fossa. The drain will be connected to a bag and fixed to the skin with a silk. Said drain will be placed at the level of the surgical bed.

Regarding the control group, intraoperative drainage will not be placed, except when the surgeon's discretion considers it necessary due to the high risk of bleeding, bile leakage or any other process / complication in which it may benefit from intra-abdominal drainage.

All patients, regardless of the randomization group, will receive a quality of life questionnaire (SF-36) prior to surgery that they must complete.

All patients will receive routine antibiotic prophylaxis 60 minutes before surgery, repeating the number of doses that are required according to blood loss and surgical time. Antibiotic prophylaxis will be adjusted according to the resistance protocols of each participating center.

○ **DATA COLLECT**

The following variables will be collected for each patient:

- **Recipient preoperative** variables: gender, age, pre-transplant stay, BMI, ASA, diabetes, HTN, dialysis, MELD, Child-Pugh, serology, albumin, bilirubin, INR, CRP, creatinine, ascites, SBP, prothrombin time, encephalopathy, time from SSI to HT (months), retransplantation, previous surgeries, cirrhosis etiology, indication for transplantation, sarcopenia.
- **Donor** characteristic variables: age, stay in ICU, vasoactive drugs, cultures, antibiotics, CIT, WIT, type of donation (DBD / DCD), previous immunosuppression.

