Subjects can withdraw at any time, with or without reason, and without prejudice to them. The subject participating in the study may revoke his consent at any time, without expression of cause and without thereby incurring responsibility or harm to the participating subject. Individuals who drop out of the study will not undergo further follow-up or be substituted. The investigator may withdraw a subject from the study if he considers that the subject can no longer comply with all the requirements of the study or if any of the procedures is considered possibly harmful to him. Data that has already been collected on withdrawn subjects will be retained and used for analysis, but no new data will be collected after withdrawal.

- **Withdrawal criteria**

Those patients who meet any of these criteria will be withdrawn from the study:

- Presence of adverse events that at the discretion of the investigator implies the withdrawal of the patient.
- Deviation from the protocol that affects the interpretation of the study results and its scientific validity.
- Optional decision.
- Resignation of the individual to continue in the study.
- Loss of follow-up.

- **TREATMENT OF SUBJECTS**

- **Description of the intervention**

In the intervention group, intra-abdominal drainage will be placed in the right flank / right iliac fossa. This drain will be placed on the surgical bed and the extracorporeal end will drain into a collection bag. Control of the amount drained and the appearance of the content will be carried out on a daily basis. If the clinical situation of the patient allows it, the drain should be removed on the 3rd postoperative day. If the clinical status or complications do not allow its withdrawal, consider withdrawing it as soon as said contraindications allow it.

The control group will not receive drainage. The evolution and the appearance of complications will be monitored in the ICU and ward on a daily basis.

The subjects will be closely monitored through the daily visit to the ICU and ward.

Regarding the assessment of quality of life (SF-36), the patient will complete a questionnaire at various points in the process:

- Inclusion on the waiting list.
- One month after surgery.
- 4 months after surgery.

- **Management of investigational medications / products.**

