- **SF-36:** Physical function, physical role, body pain, general health, vitality, social function, emotional role, mental health (on inclusion in the waiting list, one month after surgery, 4 months after surgery).

- **SUBJECT FOLLOW-UP**

As we have previously indicated, patients will be evaluated daily by the research staff during their hospital stay. Those who were discharged before day 30 post-transplant will continue to contact the researchers by phone and report any event related to the insertion point of the drain.

Calls will be made from discharge, the first 30 days every 15 days, from the month of discharge the periodicity will be monthly until 90 days from the intervention. The last follow-up call will be made on day 90.

- **SAFETY ASSESSMENT (only for medicines, food or other therapeutic procedures).**

All patients assigned to the control group (DN) will be reevaluated intraoperatively. If, for obvious clinical reasons, the placement of the drain is required, said patient will be excluded from the study (randomization will not be carried out, so it would not be included in the RCT) and the drain will be placed.

Patient safety was not impaired at any point in the study, with the intervention group (D) being the routine procedure in LT and the control group (ND) re-evaluated intraoperatively.

- **STATISTICS**

- **Data handling**

The data collection will be carried out through a Data Collection Notebook, capturing all the data in it legibly and in blue pen. Subsequently, said data will be dumped into a CRD through a spreadsheet. This sheet allows online access for the different study participants, to perform randomization and assign the patient code and to enter the data of each of the included patients. Patients will be included without personal data or identification documents, only an identification code that will be assigned to each one at the time of randomization. Once the trial is finished, all the data collected in the database will be evaluated for the writing of the final report.

All the documentation related to the study will remain stored in the Investigator's File, in the participating center, under the custody of the Principal Investigator until the end of the study. Once the study is finished, the documentation will be indexed and transferred to the general file of the center, complying with the recommendations established with respect to the Good Clinical Practice Standards.

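### The objective, main goal and arm labels contradict the one non-inferiority hypothesis the trial was sized for, and the primary analysis does not carry that hypothesis forward

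*Combined protocol and SAP*

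**What the plan says.** **Objectives.** The section on the objective and purpose opens by asking whether prophylactic drain use "reduces postoperative intra-abdominal complications, compared to their routine use". The main goal, immediately below, is "To assess whether the prophylactic use of abdominal drains in the postoperative period of LT increases the number of abdominal complications" over 90 days. The abstract asks whether routine drainage "is associated or not with an increase in postoperative complications". None of the three mentions non-inferiority. The justification text just before them does note that no randomized non-inferiority trial exists on this question.

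**Hypothesis.** The Sample size section states that "the risk of postoperative complications at 90 days in the ND group would not be higher than in group D". It explains that a non-inferiority design was chosen because leaving out the drain has advantages for patients and cost. It assumes 9% complications with a drain and 6% without, a 4% margin, alpha 0.05 and 80% power, giving 174 per arm and 365 in total.

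**Arm labels.** Study design calls ND the control group and D simply the drainage group. Description of the intervention says "In the intervention group, intra-abdominal drainage will be placed in the right flank / right iliac fossa" and that controls get no drain. Safety assessment also labels ND the control and, in one sentence, has both labels for the other arm: "with the intervention group (D) being the routine procedure in LT".

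**Primary analysis.** Analysis of the main variable names only a comparison of the incidence of postsurgical complications by Clavien-Dindo. The Descriptive analysis section supplies a general rule of chi-square tests for qualitative variables with significance at p below 0.05.

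**The concern.** A non-inferiority conclusion depends on which arm is under test, which is the reference, and where the margin lies. Here the sections that should fix these things point elsewhere. The objective names no drain-free comparator, the objective and main goal run in opposite directions, and the labels describe standard care as the intervention.

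Usually a clear primary analysis would settle the matter. This one does not repeat the hypothesis or the margin, and the only decision rule in the statistics section is p below 0.05 on a chi-square test. An analyst who follows the objectives and that rule would run a test of difference, for which the trial was not sized. A non-significant result would then be likely even if the planning assumptions were correct, and it could be misread as either equivalence or failure. If the direction and rule are settled only after data are available, the choice will also be open to the suspicion that it was made to suit them.

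**Working it through.** **Inputs (Sample size section).** Complication risk 0.09 in D and 0.06 in ND; margin 0.04; alpha 0.05; power 80%; 174 per arm. Two assumptions are needed: the margin is an absolute risk difference, and alpha is one-sided. The protocol states neither.

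**1. Reproduce the plan's figure: ND non-inferior to D.**
- Variance sum: 0.09 × 0.91 + 0.06 × 0.94 = 0.0819 + 0.0564 = 0.1383.
- Distance from the expected difference to the margin: 0.04 + (0.09 − 0.06) = 0.07.
- n per arm = 0.1383 × (1.645 + 0.842)² / 0.07² = 174.5, so 175 against the stated 174.
- Inflation: 348 × 1.05 = 365.4, matching the stated 365.
- Power at 174: SE = √(0.1383/174) = 0.0282; Φ(0.07/0.0282 − 1.645) = 79.9%.

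With one-sided alpha 0.025 the requirement is 222 per arm, and power at 174 is 69.9%. The stated figure therefore corresponds to one-sided 0.05.

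**2. Superiority, the natural test of reduces or increases.** The usual two-proportion formula is used, with pooled variance under the null: 2 × 0.075 × 0.925 = 0.13875.
- n per arm, two-sided 0.05 = (1.960 × √0.13875 + 0.842 × √0.1383)² / 0.03² = 1,209.
- Power at 174 = Φ((0.03 × √174 − 1.960 × √0.13875) / √0.1383) = 18%.
- One-sided 0.05: 953 per arm; power at 174 about 28%.

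| Question | Needed per arm | Power at 174 |
|---|---|---|
| ND non-inferior to D, one-sided 0.05 | 175 | 79.9% |
| D and ND differ, two-sided 0.05 | 1,209 | 18% |
| One-directional superiority, one-sided 0.05 | 953 | 28% |

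**3. The same data under the two rules.** Suppose the observed risks equal the planning rates.
- Non-inferiority: ND minus D is −3 points, and its upper limit is −3 + 1.645 × 2.82 = +1.6 points. This is below 4, so non-inferiority is concluded.
- Superiority: z = 0.03 / √(0.13875/174) = 1.06, short of 1.96, so no significant difference is reported.

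The choice of rule decides what the trial reports.

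**4. Arm roles by section.**

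| Section | D | ND |
|---|---|---|
| Study design | drainage group | control |
| Description of the intervention | intervention | control |
| Safety assessment | intervention, also routine procedure | control |
| Sample size (by its hypothesis) | reference | test |

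**The case against.** The strongest reply is that the hypothesis is not in doubt. The Sample size section states one, names the arms as D and ND rather than intervention and control, and gives a reason for the direction. The stated 174 reproduces under that hypothesis and not under the superiority alternatives. Calling the arm that receives a device the intervention is a common habit and alters no allocation or estimate. The objective and main goal, though worded in opposite directions, are both answered by the sign of one risk difference. The odd sentence in the objective may be a drafting or translation slip, although that is only an inference.

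Most of this stands, and it rules out three stronger readings:
- A reader might infer that the trial has no single non-inferiority hypothesis. It has exactly one, in the Sample size section.
- A reader might infer from the labels that the test runs in reverse, D against ND. Power would then be Φ(0.01/0.0282 − 1.645), about 10%. No section specifies that test, and the Safety assessment identifies D as routine care, so this figure is not a loss in this trial.
- A reader might infer that D is called the intervention throughout. Study design does not do so.

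What the reply does not meet is the gap in the primary analysis. One risk difference can answer both the objective and the main goal, but neither of them is a non-inferiority question, and the only stated decision rule is a test of difference.

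**Conclusion.** The objective, the main goal and the arm labels are inconsistent with the single hypothesis in the Sample size section, and the primary analysis does not restate that hypothesis. This is more than clerical, because following the objectives and the general p-value rule leads to a question with about 18% power (two-sided 0.05) in place of one with about 80%. Both figures take the planning rates of 9% and 6% as true. The 80% also assumes an absolute 4-point margin and one-sided alpha 0.05.

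The intended design can be recovered from the protocol, so the defect is in how it is stated. It should be corrected before analysis. It gives no reason to change the sample size.

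**What to change.** 1. Replace the objective and the main goal with one statement, and align the abstract with it: the trial assesses whether omitting the drain (ND, test arm) is non-inferior to routine drainage (D, reference arm) for the 90-day primary complication endpoint.
2. Word that endpoint identically in the objectives, Sample size and Analysis of the main variable. At present these refer respectively to abdominal complications; to postoperative complications and early transplant-related complications; and to postsurgical complications. The sponsor must choose one and confirm that the 9% and 6% apply to it.
3. Label D as reference and ND as experimental in Study design, Description of the intervention and Safety assessment.
4. In Analysis of the main variable, state that non-inferiority is concluded if the upper confidence limit for the risk difference ND minus D, at the alpha used for sizing, lies below 4 percentage points. Meeting the margin with the point estimate is not enough. If the sizing alpha was one-sided 0.05, as the 174 implies, this is the upper limit of a two-sided 90% interval. The protocol should say so.

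The cost is a wording amendment. Allocation, data collection and the 365 patients are unaffected.
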